### 8.3 Scientific and Statistical Considerations

The overall bioequivalence (BE) recommendations for this product are *in vitro* and *in vivo* (pharmacokinetic [PK] and pharmacodynamic [PD]) studies. Bioequivalence assessment of dry powder inhalers is complicated because delivery to the sites of action in the lung does not occur primarily after systemic absorption. As such, this locally-acting product is intended to produce its effect upon delivery to sites in the lung without relying on systemic absorption, though systemic absorption may contribute to its clinical effect. For these reasons, *in vitro* studies coupled with a PK and PD study are required to determine the delivery of drug substance to sites of action in the lung. This study satisfies the PD regulatory requirements of the clinical studies.

### 8.4 Justification for Use of Placebo

The FDA Draft Guidance on fluticasone propionate; salmeterol xinafoate powder/inhalation product recommends that all subjects participate in a placebo run-in period to wash out any pre-study corticosteroids/LABAs and establish baseline FEV1 values.

A Placebo group is included in the active treatment period of the study to confirm the sensitivity of the study and minimize the possibility of a false positive result of therapeutic equivalence. Therefore, in addition to demonstrating therapeutic equivalence between Test and Reference products, both active products must show statistical superiority to the Placebo. Eligible subjects will have an

chance of being randomized to Placebo (**randomization** scheme of Test: Reference: Placebo).

All subjects will be dispensed a rescue inhaler to treat sudden asthma symptoms during the placebo run-in and active treatment periods of the study.

### 8.5 Risks and Benefits

The risks and benefits to subjects enrolled in clinical research studies that include a Placebo treatment group must be carefully considered based on three main criteria, namely: the disease being treated, the availability, efficacy and safety of already approved therapies and the scientific and statistical requirements of the desired outcome of the research study. The Office of Human Rights Protection, a Division of the US Federal Government's Department of Health and Human Services, has issued a detailed guidebook to Institutional Review Boards (IRBs) that includes discussion on the use of Placebos in clinical studies.

A Randomized, Multiple-Dose, Blinded, Placebo-Controlled, Parallel-Design, Multiple-Center, Clinical Study to Evaluate the Therapeutic Equivalence of Fluticasone Propionate and Salmeterol Inhalation Powder, 100 mcg/50 mcg (Supplied by Teva Pharmaceuticals Ireland) to ADVAIR DISKUS® 100/50 (fluticasone propionate/salmeterol) Inhalation Powder, (GlaxoSmithKline) in Subjects With Asthma

All subjects enrolled in this study will receive the benefit of free specialized medical care beyond standard medical treatment that would be expected through most health insurance plans. In addition, the subject will receive a stipend for participation to cover costs and expenses associated with trips to the medical facility.

### 9.0 STUDY OBJECTIVES

The objectives of this study are to:

- Evaluate the therapeutic equivalence of a generic Fluticasone Propionate and Salmeterol Inhalation Powder, 100 mcg/50 mcg (Supplied by Teva Pharmaceuticals Ireland) to ADVAIR DISKUS® 100/50 (fluticasone propionate and salmeterol) Inhalation Powder, (GlaxoSmithKline) in subjects with asthma.
- 2. Demonstrate the superiority of the Test and Reference (active) treatments over Placebo treatment in subjects with asthma.

### **10.0 INVESTIGATIONAL PLAN**

#### Study Design and Plan Description

This randomized, multiple-dose, blinded, placebo-controlled, parallel-design, multiple-center, clinical endpoint study has been designed to evaluate the clinical (therapeutic) effect of generic Fluticasone Propionate and Salmeterol Inhalation Powder, 100 mcg/50 mcg (Supplied by Teva Pharmaceuticals Ireland) to ADVAIR DISKUS® 100/50 (fluticasone propionate and salmeterol) Inhalation Powder, (GlaxoSmithKline) in subjects with asthma.

Following a 14-21 day placebo run-in period, subjects who continue to meet inclusion/exclusion criteria will be randomized in a ratio (Test: Reference: Placebo) for  $28 \pm 2$  days of treatment. Approximately subjects will enter the run-in period to randomize approximately subjects to the active treatment period of the study. To qualify for inclusion in the study, subjects must be  $\geq 12$  years and  $\leq 75$  years of age, with a diagnosis of asthma as defined by the National Asthma Education and Prevention Program (NAEPP) guidelines at least 12 weeks before Screening.

Before any study-specific procedures are performed, all subjects will read and sign the IRB-approved informed consent form (ICF) or assent, as applicable.

Eligible subjects will complete the clinic visits as follows:

- Visit 1: Screening
  - Visit 1a: General Screening
  - Visit 1b: Screening (Day -21 to -14).

A Randomized, Multiple-Dose, Blinded, Placebo-Controlled, Parallel-Design, Multiple-Center, Clinical Study to Evaluate the Therapeutic Equivalence of Fluticasone Propionate and Salmeterol Inhalation Powder, 100 mcg/50 mcg (Supplied by Teva Pharmaceuticals Ireland) to ADVAIR DISKUS® 100/50 (fluticasone propionate/salmeterol) Inhalation Powder, (GlaxoSmithKline) in Subjects With Asthma

Following completion of Screening procedures, qualified subjects will enter into Placebo Run-in: (14-21 days prior to Day 1).

- Visit 2: Randomization (Day 1)
- Visit 3: End of Study (Day  $29 \pm 2$ )/Early Termination

#### Screening

Screening evaluations will be performed in accordance with the study schematic. Safety assessments will include: vital sign measurement, height, weight, physical examination, serum pregnancy test (for all women of childbearing potential), drug, alcohol, and cotinine testing, 12-lead electrocardiogram (ECG), and clinical laboratory evaluations. Clinical assessments will include FEV1 taken at each visit.

orced Volume Vital

Capacity (FVC) and FEV1/FVC ratio [(FEV1/FVC) x 100] will be recorded with FEV1 measurements at each visit. Pre-bronchodilator FEV1 at Screening must be 40%-85% (including these values) of predicted value. Once a qualifying FEV1 is obtained, puffs **100** puffs **100**; 90 mcg per puff, pressurized metered-dose inhaler) of albuterol inhalation will be administered (at each inhalation, the breath is held for 5-10 second before the subject exhales; four separate doses are delivered at approximate 30 seconds intervals) and spirometry will be repeated starting approximately 15 minutes from the last inhalation. The subject must demonstrate at least 15% reversibility of FEV1 within 30 minutes after albuterol administration to qualify for inclusion in the study. Post bronchodilator vital signs will be obtained.

Following completion of Screening procedures, qualified subjects will enter into Placebo Run-in: (14-21 days prior to Day 1).

#### Enrollment

Eligible subjects will be enrolled in a placebo run-in period for 14-21 days to establish baseline  $FEV_1$  values. Subjects will be dispensed an inhaler containing Placebo product to be administered twice daily. Subjects must administer at least  $\square$  of the required doses during the run-in period to be eligible for randomization. Subjects will also receive an albuterol inhaler to be used as a rescue medication throughout the study.

A Randomized, Multiple-Dose, Blinded, Placebo-Controlled, Parallel-Design, Multiple-Center, Clinical Study to Evaluate the Therapeutic Equivalence of Fluticasone Propionate and Salmeterol Inhalation Powder, 100 mcg/50 mcg (Supplied by Teva Pharmaceuticals Ireland) to ADVAIR DISKUS® 100/50 (fluticasone propionate/salmeterol) Inhalation Powder, (GlaxoSmithKline) in Subjects With Asthma

#### **Randomization**

Subjects who meet all inclusion/exclusion and randomization criteria at Visit 2 will be randomized to study product in a ratio (Test: Reference: Placebo). Serial pulmonary function tests will be performed over 12 hours at Visit 2. FEV1 should be measured at approximately

) before the first dose of study product and approximately 30 minutes, 1, 2, 3, 4, 6, 8, 10, and 12 hours post-dose. The second dose of study product will be administered after the 12-hour FEV1 is collected. At least two of the pre-dose FEV1 measurements must meet ATS criteria for quality to be acceptable. The average of the acceptable FEV1 measurements will be used to determine the baseline FEV1, which must be  $\geq 40\%$  and  $\leq 85\%$  of predicted normal value and may not vary by more from the qualifying Screening visit FEV1 value at Visit 2 for the subject to be eligible for inclusion in the study.

#### End of Study

The final three  $FEV_1$  measurements will be collected at Visit 3. The first  $FEV_1$  should take place at the same time of day as the **second second second** 

Subjects should not administer the rescue medication, or study product within 6 hours before any study visit.

#### **10.1 Selection of Study Design**

The study was designed based on the FDA Draft Guidance on fluticasone propionate; salmeterol xinafoate powder/inhalation product, and generally accepted standards for the conduct of bioavailability and bioequivalence studies.

#### **10.2 Selection of Study Population**

#### **10.2.1 Inclusion Criteria**

- 1. Male or non-pregnant, non-lactating female,  $\geq 12$  years and  $\leq 75$  years of age.
- 2. Signed informed consent form that meets all criteria of current Food and Drug Administration (FDA) regulations. For subjects who are considered minors in the state the study is being conducted (< 18 years in most states), the parent or legal guardian should sign the consent form and the child will be required to sign a subject "assent" form.
- 3. Body mass index (BMI) between 18 kg/m^2 and 39 kg/m^2, inclusive, for subjects > 18 years old. For subjects 12 to 18 years old, BMI between 15 kg/m^2 and 35 kg/m^2, inclusive.
- 4. Female subjects who are of non-childbearing potential must meet one of the following criteria:

A Randomized, Multiple-Dose, Blinded, Placebo-Controlled, Parallel-Design, Multiple-Center, Clinical Study to Evaluate the Therapeutic Equivalence of Fluticasone Propionate and Salmeterol Inhalation Powder, 100 mcg/50 mcg (Supplied by Teva Pharmaceuticals Ireland) to ADVAIR DISKUS® 100/50 (fluticasone propionate/salmeterol) Inhalation Powder, (GlaxoSmithKline) in Subjects With Asthma

- surgically sterile (e.g., bilateral oophorectomy, tubal ligation, hysterectomy or permanent sterilization procedures), with the procedure performed at least 3 months before initial dosing
- naturally postmenopausal (no menses) for at least 1 year before initial dosing and/or has a documented FSH level  $\geq$  40 mIU/mL at screening
- pre-menarchal
- 5. Females of childbearing potential must not be pregnant or lactating at Screening or Randomization as confirmed by a negative serum pregnancy test with a sensitivity of 25 mIU/mL of human chorionic gonadotropin at Screening and a negative urine pregnancy test with a sensitivity of less than 50 mIU/mL at all other visits.

Women of childbearing potential must agree to the use of a reliable method of contraception (e.g., total abstinence, intrauterine device, a double-barrier method, oral, transdermal, injected or implanted non- or hormonal contraceptive), throughout the study. A sterile sexual partner is not considered an adequate form of birth control. Subjects on hormonal contraceptives must have been on the same hormonal contraceptive for at least one month before the Screening and continue throughout the duration of the study.

- 6. Diagnosis of asthma (based on National Asthma Education and Prevention Program [NAEPP] guidelines) at least 12 weeks before Screening.
- 7. Pre-bronchodilator  $FEV_1 \ge 40\%$  and  $\le 85\%$  of predicted at Screening and Randomization.
- 8. Airway reversibility  $\geq 15\%$  of FEV1 within 30 minutes after receiving puffs of albuterol inhalation (**matrix**, pressurized metered-dose inhaler) at Screening.
- 9. Able to discontinue use of their asthma medications during the run-in period and for the remainder of the study.
- 10. Able to replace current short-acting beta-agonists [SABAs] with the study supplied salbutamol/albuterol rescue inhaler for use as needed for the duration of the study. Subjects must be able to withhold all SABAs for at least 6 hours before lung function assessments on study visits.
- 11. Able to continue on stable regimen of the ophylline for the duration of the study and able to withhold the ophylline as judged by the Investigator for the required time intervals before study visits. See Section 10.2.4 for required washouts.
- 12. Able to discontinue oral corticosteroids, parenteral corticosteroids and oral SABAs for the time intervals before study visits as specified in Section 10.2.4.

A Randomized, Multiple-Dose, Blinded, Placebo-Controlled, Parallel-Design, Multiple-Center, Clinical Study to Evaluate the Therapeutic Equivalence of Fluticasone Propionate and Salmeterol Inhalation Powder, 100 mcg/50 mcg (Supplied by Teva Pharmaceuticals Ireland) to ADVAIR DISKUS® 100/50 (fluticasone propionate/salmeterol) Inhalation Powder, (GlaxoSmithKline) in Subjects With Asthma

- 13. Able to perform valid and reproducible pulmonary function tests as per ATS (American Thoracic Society) including no evidence of spirometry effort-induced bronchoconstriction.
- 14. Currently non-smoking (including vapor cigarettes), no use of any tobacco products within 1 year prior Screening and has  $\leq$  10 pack-years smoking of historical use (i.e., one pack per day for 10 years).
- 15. Ability to use the inhalation products correctly.

#### **10.2.2 Exclusion Criteria**

- Life-threatening asthma, defined as a history of asthma episode(s) requiring intubation, and/or associated with hypercapnoea; respiratory arrest or hypoxic seizures, asthma related syncopal episode(s), or asthma-related hospitalizations within one year before Screening or during the run-in period.
- 2. Allergy or significant history of hypersensitivity, idiosyncratic reactions, or intolerance to any sympathomimetic drug (e.g., salmeterol or albuterol), or any inhaled, intranasal, or systemic corticosteroid therapy, or milk proteins.
- 3. History of cystic fibrosis, bronchiectasis, or co-morbid respiratory or sinus diseases, including chronic obstructive pulmonary disease, chronic bronchitis, emphysema, tuberculosis, pulmonary carcinoma, pulmonary fibrosis, pulmonary hypertension that, in the opinion of the Investigator, would compromise subject safety or interfere with the evaluations.
- 4. Evidence of viral or bacterial upper or lower respiratory tract infections (e.g., pneumonia, viral bronchitis, sinobronchitis, etc.), sinus infection, or middle ear infection within four weeks before Screening or during the run-in period.
- 5. Current evidence or history of cardiovascular disorders, including uncontrolled hypertension, uncontrolled coronary artery disease, known aortic or cerebral aneurysm, myocardial infarction or stroke, and/or current coronary insufficiency that, in the opinion of the Investigator, would compromise subject safety or interfere with the evaluations.
- 6. Cardiac arrhythmia or 12-lead ECG abnormalities that, in the opinion of the Investigator, would compromise subject safety or interfere with the evaluations; or a
- 7. Subjects receiving or who may require during the study non-potassium sparing diuretics or medications with the potential to affect the course of asthma or to interact with sympathomimetic amines within 30 days before Screening. Examples include but not limited to beta blockers, oral decongestants, benzodiazepines, digitalis, phenothiazines, polycyclic antidepressants, monoamine oxidase inhibitors.
- 8. History of posterior subcapsular cataracts or glaucoma that, in the opinion of the Investigator, would compromise subject safety.

- 9. Any clinically significant finding on physical exam or clinical labs that, in the opinion of the Investigator, would compromise subject's safety or data integrity.
- 10. History or current evidence of significant renal, hepatic, cardiovascular (including ECG with evidence of ischemic heart disease, congestive heart failure, and cardiac dysrhythmia), neurologic, hematologic, endocrine, psychiatric dysfunction, or any other significant medical illness or disorder in the opinion of the Investigator, would compromise subject safety or interfere with the evaluations.
- 11. History of convulsive disorders.
- 12. History within the past 6 months, or current evidence of hyperthyroidism.
- 13. History within the past 6 months, or current evidence of uncontrolled diabetes.
- 14. History of paradoxical bronchospasm.
- 15. Use of inhaled SABAs within 6 hours before Screening or use of rescue medication within 6 hours before Randomization.
- 16. Use of oral SABAs within before Screening.
- 17. Use of oral or parenteral corticosteroids within before Screening.
- 18. Use of muscarinic beta2-agonists (MABAs), ipratropium bromide, or ipratropium bromide with albuterol within before Screening.
- 19. Use of cromolyn sodium within before Screening.
- 20. Use of antihistamines (other than cetirizine, desloratadine, or diphenhydramine), including fexofenadine and loratadine, within before Screening or Randomization.
- 21. Use of cetirizine within before Screening or Randomization.
- 22. Use of desloratadine within before Screening or Randomization.
- 23. Use of diphenhydramine within before Screening or Randomization.
- 24. Use of inhaled long-acting beta2-agonists (LABAs) (e.g., salmeterol, formoterol) or combination products containing bronchodilators (e.g., Symbicort) within before Screening.
- 25. Use of tiotropium within before Screening.
- 26. Exercise within before Screening.
- 27. Use of leukotriene modifiers within before Screening.
- 28. Any surgery within 6 months before Screening that, in the opinion of the Investigator, would compromise subject safety or integrity of the study data.

A Randomized, Multiple-Dose, Blinded, Placebo-Controlled, Parallel-Design, Multiple-Center, Clinical Study to Evaluate the Therapeutic Equivalence of Fluticasone Propionate and Salmeterol Inhalation Powder, 100 mcg/50 mcg (Supplied by Teva Pharmaceuticals Ireland) to ADVAIR DISKUS® 100/50 (fluticasone propionate/salmeterol) Inhalation Powder, (GlaxoSmithKline) in Subjects With Asthma

- 29. Biological treatment for asthma, approved or investigational **before** Screening and throughout the study.
- 30. Receipt of any drug as part of a research study within 30 days before Screening.
- 31. Positive test results for drugs of abuse, alcohol or cotinine at screening.
- 32. Employees of the Investigator or research center or their immediate family members.
- 33. Previous participation in this study.
- 34. Inability to understand the requirements of the study and the relative information and are unable or not willing to comply with the study protocol.

### 10.2.3 Randomization Inclusion/Exclusion

At the end of the Run-in period subjects will be randomized to treatment if they continue to meet all of the general inclusions criteria and do not meet any of the general exclusion criteria. In addition, they must also meet all following inclusion criteria and do not meet any of the following exclusion criteria.

#### Randomization inclusion criteria:

- 1. Compliance with the Run-in placebo treatment dosing as evaluated via the diary entries.
- 2. Minimum of 2 acceptable, as determined by ERT spirometry as meeting all ATS criteria, predose FEV1 measurements needed to establish baseline.
- 3. Calculated baseline FEV1 must be  $\geq$  40% and  $\leq$  85% of predicted normal value.

#### Randomization exclusion criteria:

- 1. Occurrence of clinically significant asthma exacerbations according to the pre-defined criteria (see Section 10.2.6).
- 2. Viral or bacterial, U/LRTI or sinus or middle ear infection during the Run in Period, or on the first day of treatment.
- 3. Use of prohibited medications during the placebo run-in period (see Washout Table in Section 10.2.4).
- 5. Coexisting of all occurrences liver injury that meets Hy's law criteria, defined as: alanine aminotransferase (ALT) or aspartate aminotransferase (AST) elevation of > 3x the upper

A Randomized, Multiple-Dose, Blinded, Placebo-Controlled, Parallel-Design, Multiple-Center, Clinical Study to Evaluate the Therapeutic Equivalence of Fluticasone Propionate and Salmeterol Inhalation Powder, 100 mcg/50 mcg (Supplied by Teva Pharmaceuticals Ireland) to ADVAIR DISKUS® 100/50 (fluticasone propionate/salmeterol) Inhalation Powder, (GlaxoSmithKline) in Subjects With Asthma

limit of normal (ULN), total bilirubin elevation of > 2x ULN, and the absence of initial findings of cholestasis (i.e. no substantial increase of alkaline phosphatase [ALP]).

A Randomized, Multiple-Dose, Blinded, Placebo-Controlled, Parallel-Design, Multiple-Center, Clinical Study to Evaluate the Therapeutic Equivalence of Fluticasone Propionate and Salmeterol Inhalation Powder, 100 mcg/50 mcg (Supplied by Teva Pharmaceuticals Ireland) to ADVAIR DISKUS® 100/50 (fluticasone propionate/salmeterol) Inhalation Powder, (GlaxoSmithKline) in Subjects With Asthma

### 10.2.4 Restrictions During the Study

The following medications will not be allowed prior to Screening for the respective time intervals through the run-in period and for the duration of the study (see details and exceptions where applicable):

A Randomized, Multiple-Dose, Blinded, Placebo-Controlled, Parallel-Design, Multiple-Center, Clinical Study to Evaluate the Therapeutic Equivalence of Fluticasone Propionate and Salmeterol Inhalation Powder, 100 mcg/50 mcg (Supplied by Teva Pharmaceuticals Ireland) to ADVAIR DISKUS® 100/50 (fluticasone propionate/salmeterol) Inhalation Powder, (GlaxoSmithKline) in Subjects With Asthma

Subjects will be requested to refrain from consuming caffeine containing products such as coffee, tea, cola drinks, energy drinks, or chocolate within **and the set of any study visit**, if possible. On Visit 2, subjects will also be requested to refrain from consuming caffeine-containing products until the last point of the spirometry at Visit 2, if possible.

## 10.2.5 Removal of Subjects from the Study

Subjects will be advised that they are free to withdraw from the study at any time for any reason or, if necessary, the Investigator may withdraw a subject from the study to protect the health of that subject. A subject may also be withdrawn for not complying with study procedures. The clinical report will include all reasons for early withdrawals.

If a randomized subject terminates from the study early, all efforts will be made to complete their next scheduled visit to perform all required End of Study/ Early termination visit activities except spirometry that does not need to be performed. In case of early termination the Investigator will fully document the reason for early termination. Reasons for early termination may include the following:

- Subject withdrew consent.
- Significant AE that led the Investigator or subject to withdraw for safety reasons.
- Serious AE, regardless of relationship to study medication.
- Non-compliance with protocol requirements (e.g., use of restricted medication, not following dosing procedures, failure to make scheduled study visits in a timely fashion).
- Pregnancy
- Significant worsening of asthma, defined as a clinically significant exacerbation (see Section 10.2.6) that requires emergency intervention, treatment with restricted medications or hospitalization. Withdrawal of the subject from the study is based on Investigator judgment if he or she believes it is in the best interest of the subject to withdraw from the study and provided alternative treatment.
- Excessive use of rescue albuterol during the study. See Section 10.2.6.

A Randomized, Multiple-Dose, Blinded, Placebo-Controlled, Parallel-Design, Multiple-Center, Clinical Study to Evaluate the Therapeutic Equivalence of Fluticasone Propionate and Salmeterol Inhalation Powder, 100 mcg/50 mcg (Supplied by Teva Pharmaceuticals Ireland) to ADVAIR DISKUS® 100/50 (fluticasone propionate/salmeterol) Inhalation Powder, (GlaxoSmithKline) in Subjects With Asthma

- Subject requires the use of rescue medication during serial spirometry at Visit 2.
- Participant enrolls in another clinical trial, or is found to have previously enrolled in this clinical trial.

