## 10.4.6 Visit 3: End of Study (Day 29 ± 2)/Early Termination

- 1. Vital Signs: BP, HR, RR, and temperature will be collected.
- 2. Physical Exam: Perform an examination of head, ear, eyes, nose, throat, and lungs.
- 3. Urine Pregnancy Test: All females of childbearing potential will have a urine pregnancy test performed.
- 4. **Clinical Laboratory Testing:** All subjects will have a blood sample taken for hematology and clinical chemistry testing and a urine sample for urinalysis.
- 5. **12-Lead ECG**: Subjects will undergo a 12-lead ECG to screen for significant changes in cardiothoracic findings.
- 6. **Collect and Review Diary**: Diaries will be collected and reviewed for compliance with protocol requirements.
- 7. **Concomitant Medications**: Subjects will be questioned about any changes in concomitant medication use since the last visit. The subjects will also be questioned regarding washout of drugs prior to lung function testing.
- 8. Adverse Events: Subjects will be questioned about AEs since the last visit.
- 9. Spirometry: The final FEV1 measurements will be collected. The first FEV1 should occur at the same time of day as the FEV1 pre-dose measurement, respectively, collected at Visit 2 (± 2 hours). The remaining FEV1 measurements should be collected at following the preceding measurement.
- 10. Pulse Oximetry: Pulse oximetry will be measured during the spirometry testing.
- 11. Collect Study Product/Rescue Medication: All study product and rescue medication inhalers will be collected.

The

A Randomized, Multiple-Dose, Blinded, Placebo-Controlled, Parallel-Design, Multiple-Center, Clinical Study to Evaluate the Therapeutic Equivalence of Fluticasone Propionate and Salmeterol Inhalation Powder, 100 mcg/50 mcg (Supplied by Teva Pharmaceuticals Ireland) to ADVAIR DISKUS® 100/50 (fluticasone propionate/salmeterol) Inhalation Powder, (GlaxoSmithKline) in Subjects With Asthma

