# NOVUM PHARMACEUTICAL RESEARCH SERVICES STATISTICAL ANALYSIS PLAN

Fluticasone Propionate and Salmeterol Inhalation Powder	Protocol No. 71736001
Subjects who discontinue due to Lack of Efficacy will be included us Section 8.2.1.	sing LOCF, as described in
Subjects taking fewer than or more than the required treatment period will be considered non-compliant with dosing ar protocol (PP) population. Compliance with number of doses will Management from ERT data and verified by the use of the diaries. active treatment period of the study are as outlined in the table below:	ll be determined by Data Compliance criteria for the
Protocol deviations will be derived algorithmically as well as report	ted by sites. Each protocol
Specific deviation and their severity are defined in the separate document.	Protocol Deviations List
Subjects with protocol deviations identifying them as participating in	the study on more than one

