# Calculation of Baseline-adjusted Pre-dose FEV1 at End of Treatment.

The endpoint of Baseline-adjusted pre-dose  $FEV_1$  at end of treatment will be calculated as  $[FEV_1]$  at end of treatment will be defined as the

If a subject has no pre-dose assessment at Visit 3, Day 29, in the mITT analysis Average  $FEV_1$  at end of treatment will be imputed (following LOCF rule) as the average of available predose assessments on the last post-baseline day (Day 2 through 32) when at least one pre-dose  $FEV_1$  assessment is available (e.g. the Early Termination visit). Only assessments occurring after start of the randomized treatment (Day 2) and up to day will be considered for LOCF. In the PP

Fluticasone Propionate and Salmeterol Inhalation Powder Protocol No. 71736001

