### 8.5 Methods for Handling Missing Data

For demographic and baseline characteristics, each variable will be analyzed using all available data. Subjects with missing data will be excluded only from analyses for which data are not available.

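### Protocol 10.2.5 waives the early-termination spirometry that Protocol 10.4.6 lists, so the SAP's Day 29 carry-forward rule may have no required FEV1 to use

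*Protocol*

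**What the plan says.** - **Protocol 10.2.5 (Removal of Subjects).** A randomized subject who stops early is asked to come to the next scheduled visit "to perform all required End of Study/ Early termination visit activities except spirometry that does not need to be performed".
- **Protocol 10.4.6.** The procedure list headed "Visit 3: End of Study (Day 29 ± 2)/Early Termination" serves both completers and early terminators. Item 9 reads "Spirometry: The final FEV 1 measurements will be collected", and no exception for early terminators is visible.
- **SAP 8.2.1 (pre-dose FEV1 at end of treatment).** In the modified intent-to-treat (mITT) analysis, a missing Day 29 value is replaced by the average from the last post-baseline day on which a pre-dose "assessment is available (e.g. the Early Termination visit"). The source days are limited: "Only assessments occurring after start of the randomized treatment (Day 2") and later, up to a day that is not legible.
- **SAP 7 (PP population).** "Subjects who discontinue due to Lack of Efficacy will be included" by LOCF, with a reference to Section 8.2.1.
- **SAP 8.2.2 and 8.2.3.** Equivalence is judged in PP, with both co-primary 90% intervals required to lie within 80.00-125.00%. Superiority to placebo is judged in mITT.
- **SAP 8.5.** After a sentence on demographic and baseline variables it adds: "Subjects with missing data will be excluded only from analyses for which data are not available".

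**The concern.** One protocol section tells the site that the test is unnecessary, and another lists it for the same visit. The SAP then builds its handling of early terminators on the result of that test. The SAP chose to keep lack-of-efficacy discontinuations in the population where equivalence is decided. If those subjects have no FEV1 after Day 1, the rule that should keep them cannot be applied. The Day 29 comparison could then rest on subjects with Visit 3 spirometry alone, which is not what SAP 7 states. The loss would be related to outcome, because worsening asthma and excessive rescue use are among the termination reasons in Protocol 10.2.5.

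**Working it through.** **Step 1: which FEV1 values can feed LOCF?** The plan gives no figure to reproduce, so this is a check of the schedule against the LOCF window (Day 2 onward).

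| FEV1 source after randomization | In the LOCF window? | Required for an early terminator? |
|---|---|---|
| Visit 2, Day 1, pre-dose and 30 min to 12 h post-dose | No | Yes |
| Visit 3/Early Termination, following 10.4.6 | Yes | Yes, if the subject attends |
| Visit 3/Early Termination, following 10.2.5 | Yes | No |
| Unscheduled visit (Protocol 10.2.6 allows for one) | Yes, if pre-dose | No |
| Home peak flow (Protocol 10.5.14) | Not FEV1, and not analysed | Not applicable |

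No other clinic visit lies between Day 1 and Visit 3. Under 10.2.5 an early terminator has no required value in the window. Under 10.4.6 there is one visit that supplies it.

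**Step 2: does another rule fill the gap?** Protocol 11.1 lets the SAP prevail where the two documents differ, but that cannot create a measurement the site did not take. SAP 8.5 might be read as excluding subjects with missing data. Its opening concerns demographic and baseline variables, so its reach to efficacy is unclear. Applied to lack-of-efficacy discontinuations, it would contradict SAP 7.

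**Step 3: when would the ratio move?** Let p be an arm's failure proportion, m its completer mean change and f the failures' mean change. With all subjects included,

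ratio = [(1 − pT)·mT + pT·f] / [(1 − pR)·mR + pR·f].

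With equal p and equal m the ratio is 1 whatever f is, so dropping failures does no harm. Take an assumed completer change of 0.30 L in both arms:

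- 8% vs 4% failures, f = 0: 0.92/0.96 = 0.958.
- 8% vs 4%, f = −0.30 L: (0.276 − 0.024)/(0.288 − 0.012) = 0.252/0.276 = 0.913.
- 4% vs 8%, f = −0.30 L: 0.276/0.252 = 1.095, the opposite direction.

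**Step 4: illustration of the verdict.** Every input is assumed: 350, 400, 500 or 600 per active arm; SD 0.25 or 0.30 L; Reference completer change 0.30 L; f of 0, −0.15 or −0.30 L. That is 4 × 2 × 3 = 24 cells per entry. The all-subjects variance is that of the completer/failure mixture, (1 − p)s² + p·sf² + p(1 − p)(m − f)², with sf = 0 when f = 0 and sf = s otherwise. Completers have n(1 − p) subjects. The 90% Fieller limits are the roots θ of (mT − θmR)² = t²(vT + θ²vR), where v is the variance of the arm mean. Entries count cells where the 80-125% verdict differs between completers only and all subjects.

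| Test vs Reference failures | Completer ratio 1.00 | Completer ratio 0.95 |
|---|---|---|
| 4% vs 4% | 0/24 | 0/24 |
| 8% vs 8% | 0/24 | 1/24 |
| 6% vs 4% | 0/24 | 6/24 |
| 8% vs 4% | 4/24 | 16/24 |
| 4% vs 6% | 0/24 | 0/24 |
| 4% vs 8% | 4/24 | 0/24 |

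The total is 31 of 288, and completers pass in every cell. By failure change the split is 1/96 at zero, 8/96 at −0.15 L and 22/96 at −0.30 L. One cell as an example: 8% vs 4%, completer ratio 1.00, f = −0.30 L, SD 0.30 L, n = 350 gives 0.778-1.068 for all subjects and 0.879-1.137 for completers. At n = 600 the all-subjects interval is 0.808-1.029, which passes.

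**Step 5: how firm is that count?** Changing only the assumed Reference completer change gives 8 of 288 at 0.40 L, 13 at 0.35, 31 at 0.30, 68 at 0.25 and 115 at 0.20. The count follows the assumption.

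**The case against.** The best defence is that the documents can be read together. Protocol 10.2.5 makes the test optional and does not forbid it. SAP 8.2.1 imputes only where a value exists and names the Early Termination visit as an example. Protocol 12.2.4 has the Visit 3 eCRF completed for early terminators. An optional test feeding a rule that applies if a value is available is coherent. This stands, and it rules out the inference that LOCF is impossible: the rule lacks a guaranteed input, not every input. It does not remove the conflict between 10.2.5 and 10.4.6, nor the gap between an optional test and a flat statement in SAP 7 that these subjects will be included.

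A second objection also stands. The PP part of the imputation paragraph, the population definitions, SAP 8.7 and the schedule cells are not visible. SAP 8.2.2 speaks of more than one PP population, and the visible text does not show which of them the lack-of-efficacy sentence governs. A fallback may exist there. It could settle the analysis, but not which instruction the site should follow.

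Three stronger readings are tempting and are not supported:

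- *The equivalence result is biased.* That needs failure rates or completer means to differ between Test and Reference, and nothing visible says that they do. In the illustration, 24 of the 31 changed cells have one arm failing at twice the rate of the other.
- *Day 1 rescue users are lost failures.* Protocol 10.2.5 lists "Subject requires the use of rescue medication during serial spirometry at Visit 2" as a possible reason for early termination, but nothing visible classes it as lack of efficacy. Day 1 post-dose values are not pre-dose, so LOCF would not use them whatever its window.
- *Superiority is inflated.* Losing placebo failures would mostly make superiority harder to show.

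**Conclusion.** The inconsistency is real and should be fixed. Two protocol sections disagree on whether an early terminator has spirometry, and the SAP's Day 29 LOCF has no required input if the waiver is followed. Whether a treatment failure counts in a co-primary analysis would then depend on a site's choice or on an unscheduled visit.

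The size of any effect cannot be stated, because sample size, variability and dropout are blacked out. The direction is open, and with equal failure rates and equal completer means there is none. The grid shows only that a changed verdict is possible under some assumptions. It is not evidence about this trial. Confidence is medium, because the hidden PP text may bear on the point.

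**What to change.** Reconcile Protocol 10.2.5, Protocol 10.4.6, SAP 7 and SAP 8.2.1 in one of two ways.

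1. Collect the pre-dose FEV1 that LOCF uses, already listed in Protocol 10.4.6, whenever an early terminator attends.
2. If the test stays optional, state in the SAP a workable method for lack-of-efficacy discontinuations with no FEV1 after Day 1, and say whether SAP 8.5 applies to efficacy.

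In either case, report by arm how many Day 29 values are observed, carried forward and missing. If a sensitivity analysis of the Day 29 ratio is added, give the missing failures a range of assumed changes, zero and below baseline. Zero alone is the assumption that altered the verdict in only 1 of 96 illustrative cells.

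The cost is a wording change in the protocol and the SAP, one count table and, optionally, one sensitivity table. No new data field is needed. Option 1 reverses the waiver and adds a slight burden at the visit. Some values will be taken off study product or after other treatment, and subjects who do not attend will still be missing.
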